## 2.2 Dosing Rationale

Skin preparations are always exposed to opportunities of being removed after administration to the skin, such opportunities as washing the face, bathing, adhesion to clothing, or sweating resulting in dilution. To be sure that effective concentration on the

skin is maintained, it is desirable that the IMP be administered multiple times a day. In consideration of the fact that people generally wash their face and hands after getting up and when bathing at night, twice-daily administration is considered highly convenient for patients, and it may contribute to achieving the best adherence. Therefore, twice-daily administration is employed.

In the phase 1 trial in AD patients in the US (271-12-204), efficacy of OPA-15406 was suggested in the 0.3% and 1% formulations among the 0.3%, 1%, and 3% formulations tested. In the phase 2 trial in AD patients aged 10 years and older outside Japan (271-12-205), the efficacy of OPA-15406 was investigated by selecting the 0.3% and 1% formulations. The results showed that the 1% formulation had a significantly higher efficacy in the primary efficacy endpoint compared to the vehicle, and the 0.3% formulation also had a higher efficacy compared to the vehicle. Also, in adults and juveniles including children, no particular concerns were raised over safety in both the 0.3% and 1% formulations. Therefore, in the ongoing phase 2 trial in adult AD patients (aged 15 - 70 years old) in Japan, the same doses of 0.3% and 1% were selected as in the phase 2 trial outside Japan (271-12-205). Also in this trial, the same doses of 0.3% and 1% as in adults are selected in order to evaluate the safety and efficacy of OPA-15406 in pediatric AD patients (aged 2 - 14 years old) in Japan.

### **2.3 Severity Rationale**

Atopic dermatitis is mainly treated with topical drugs. However, for severe patients, oral agents and ultraviolet therapy are often combined due to an inadequate response to topical drugs alone. Therefore, this trial is designed to include patients with an IGA score of 2 (mild) or 3 (moderate) whose symptoms are controllable only by topical drugs. In the phase 1 trial (271-12-204) and phase 2 trial (271-12-205) outside Japan, efficacy and safety were both demonstrated. Also in Japan, the phase 2 trial (271-15-001) is now ongoing to evaluate efficacy and safety in adult AD patients with an IGA score of 2 (mild) or 3 (moderate).

### **2.4 Trial Objectives**

Primary objective: To evaluate the safety of 0.3% and 1% OPA-15406 ointments in pediatric patients with AD when administered twice daily for 4 weeks.

Secondary objective: To evaluate the efficacy (dose response) and pharmacokinetics of 0.3% and 1% OPA-15406 ointments in pediatric patients with AD when administered twice daily for 4 weeks.

### **3 Trial Design**

#### **3.1 Type/Design of Trial**

This is a multicenter, randomized, double-blind, vehicle-controlled, parallel-group comparison trial to evaluate the safety, efficacy, and pharmacokinetics of OPA-15406 ointment in pediatric patients with AD. This trial consists of the 0.3% OPA-15406 group, the 1% OPA-15406 group, and the vehicle group. The trial design is shown in Figure 3.1-1.

##### **(1) Screening period**

After obtaining written informed consent from the subject's legal guardian (if possible, after also obtaining informed assent from the subject), the investigator or subinvestigator will perform a screening examination. The period between the day of the screening examination and the end of the baseline examination is defined as the screening period (2-30 days). The subjects who meet the inclusion criteria and do not meet any of the exclusion criteria at the baseline examination will shift to the assessment period and will be dynamically allocated to the test product (0.3% or 1% formulation of OPA-15406) or the vehicle (placebo).

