### **3.6 Measures to Minimize/Avoid Bias**

This trial is a randomized, double-blind trial.

The IMP allocation manager will prepare a master “random allocation table” hereinafter, “randomization table”) and conduct IMP coding according to the operating procedures for randomization. Also, the IMP allocation manager will prepare an emergency code list for use in emergencies such as the occurrence of a serious adverse event.

The investigator, subinvestigator, and subjects are blind to the IMP randomization code. Except for some designated personnel, the sponsor’s trial staff, including the personnel of contract research organizations, are also unable to access the IMP randomization code during the trial period.

Prior to the trial start and unblinding, the IMP allocation manager will confirm that the IMPs are indistinguishable. The randomization table is sealed by the IMP allocation manager just after completion of IMP randomization and it is kept under strict control until unblinding after fixation of all CRFs and the database.

The emergency code list will be kept under strict control by the registration system until the end of the trial. If a medical emergency occurs in a subject and knowledge of his or her IMP randomization code is considered important for treatment, the emergency code will be broken according to the “5.7 Procedure for Breaking the Blind.”

When IMPs are recovered by the sponsor prior to unblinding, they are to be recovered sealed by the IMP manager.

The subject will be allocated using the dynamic allocation method (minimization method). Details will be specified in a separate specification prepared in advance.

The results of drug concentration measurements will not be revealed until unblinding at the end of the trial.

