- 3) For the change from baseline in IGA at Week 1, Week 2 and Week 4, mixed-model repeated measures (MMRM) analysis with factors of treatment (0.3% or 1% OPA-15406 groups, and vehicle group), timepoint, baseline IGA (mild or moderate), and interaction between treatment and timepoint will be applied with an unstructured variance covariance structure to the change from baseline up to Week 4 based on OC dataset. Kenward-Roger will be used to calculate the standard error of fixed effects and degree of freedom. The least square mean of each treatment group will be calculated by timepoint. Also, the difference in the least square means between the vehicle group and each OPA-15406 group, and the two-sided 95% confidence interval and p-value will be calculated at Week 1, Week 2 and Week 4. Analysis of covariance (ANCOVA) with factors of treatment (0.3% or 1% OPA-15406 groups, vehicle group), and baseline IGA (mild or moderate) will be applied to the change from baseline up to each timepoint based on OC and LOCF dataset. The least square mean of each treatment group will be calculated by timepoint. Also, the difference in the least square means between the vehicle group and each OPA-15406 group, and the two-sided 95% confidence interval and p-value will be calculated. Using the OC and LOCF data sets, the descriptive statistics will be calculated for measured values and changes from baseline by treatment group for each timepoint.
- 4) The change from baseline in EASI, VAS for pruritus, POEM, and affected BSA will be calculated in the same manner as the change from baseline in IGA. Except for baseline, the same MMRM and ANCOVA models as those used in the analysis of IGA will be used. For baseline, the baseline values of the respective variables will be used.

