
10.1.2 Changes From Baseline in Overall EASI Score and EASI Symptom Scores

Based on the OC data set, the change from baseline in EASI score (at Week 1, Week 2, and Week 4; if the timing of discontinuation falls within the allowable window of a timepoint, the data at discontinuation will be included as the data for the timepoint) will be analyzed using the MMRM analysis with treatment (0.3% or 1% OPA-15406 group, and vehicle group), timepoint, and interaction between treatment and timepoint as factors and baseline EASI score as a covariate. An unstructured covariance matrix will be used to model the within-subject errors and Kenward-Roger method will be used to calculate the standard error of fixed-effects and the degree of freedom. If the MMRM procedure fails to converge under unstructured covariance structure, the following structure will be used in the order of 1) heterogeneous toeplitz, 2) heterogeneous autoregressive of order 1, 3) heterogeneous compound symmetry and the first (co)variance structure converging to the best fit will be used.

The least square mean of each treatment group will be calculated by timepoint. For overall EASI score, the least square mean and the standard error will be plotted by timepoint for each treatment group. The difference in the least square mean between the vehicle group and each OPA-15406 group, and the two-sided 95% confidence interval and p-value will be calculated at Week 1, Week 2, and Week 4.

Based on the OC and LOCF data sets, ANCOVA model with treatment (0.3% or 1% OPA-15406 group, and vehicle group) as a factor and baseline EASI score as a covariate will be applied to the change from baseline up to each timepoint. The least square mean in each treatment group will be calculated by timepoint. The difference in the least square

mean between the vehicle group and each OPA-15406 group, and the two-sided 95% confidence interval and p-value will be calculated at Week 1, Week 2, and Week 4. Based on the OC and LOCF data sets, measured values and changes from baseline in IGA at Week 1, Week 2, and Week 4 will be summarized by treatment group using descriptive statistics. For the overall EASI score, the mean with standard error of measured values (in the OC and LOCF data sets) will be plotted by timepoint for each treatment group.

EASI scores for body regions (face, neck, and head; upper limbs; trunk; and lower limbs) will be analyzed in the same manner as the overall EASI score.

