10.1.3 Change From Baseline in Visual Analogue Scale for Pruritus

The change from baseline in visual analogue scale (VAS) for pruritus will be analyzed in the same manner as that in the overall EASI score or each EASI symptom score.

10.1.4 Change From Baseline in VRS for Pruritus up to Day 7

The change from baseline in VRS score for pruritus up to Day 7 will be analyzed in the same manner as that in overall EASI score or each EASI symptom score. Data will be collected at baseline, 4, 8, and 12 hours after the start of administration, 1 day after the start of administration (morning and night), and thereafter in the same manner up to Day 7 (morning). The same analysis will be performed by the time zone of assessment (morning or evening). Morning or evening will be determined based on the time label entered in the case report form (CRF), not using the timepoints defined in Table 6.4-2, except the baseline, which is irrespective of the time zone of assessment. Data will be collected at baseline, and the timepoints specified above on Day 1 to Day 7.

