10.3 Adjustments for Covariates

In the analysis of the incidence of success in IGA, the Cochran-Mantel-Haenszel test stratified by baseline IGA (mild or moderate) will be conducted.

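### Children are allocated by minimisation, but the models for EASI, VAS, VRS, POEM and affected BSA make no provision for the allocation factors, so their 95% intervals are conservative to the extent that those factors are prognostic beyond the variable's own baseline.

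*Protocol*

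**What the plan says.** **Allocation.** Protocol 3.6 is the governing text: "The subject will be allocated using the dynamic allocation method (minimization method). Details will be specified in a separate specification prepared in advance". Protocol 3.1 and SAP section 3 speak only of dynamic allocation: eligible children "will be dynamically allocated to the test product (0.3% or 1% formulation of OPA-15406) or the vehicle (placebo". Neither document names a factor, a weight or a random element.

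**Models.** For EASI, SAP 10.1.2 specifies an MMRM with treatment, "timepoint, and interaction between treatment and timepoint as factors and baseline EASI score as a covariate", and an ANCOVA with treatment and baseline EASI. VAS (SAP 10.1.3) "will be analyzed in the same manner as that in the overall EASI score or each EASI symptom score". SAP 10.1.4 to 10.1.6 say the same of VRS, POEM and affected BSA, and 10.1.7 carries the approach over to percent changes. Protocol 7.4.2 plans the same adjustment. Its item 4, on EASI, VAS, POEM and affected BSA, takes the IGA models and changes the baseline term: "For baseline, the baseline values of the respective variables will be used". Its item 5 does likewise for VRS.

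**Covariates.** SAP 10.3 has one sentence: "In the analysis of the incidence of success in IGA, the Cochran-Mantel-Haenszel test stratified by baseline IGA (mild or moderate) will be conducted". Baseline IGA also enters the models for change in IGA (SAP 10.1.1), but none of the models for the five other scales.

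**The concern.** Minimisation steers the arms towards balance on its factors, so those factors add little to the chance variation of a treatment difference. A model that omits a prognostic factor leaves its variance in the residual and computes a standard error as if the arms could still differ on it by chance. The estimate stays unbiased, but the interval covers more than 95%.

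This matters because the trial is built on estimation. SAP 6.6 sets no significance level and makes the two-sided 95% interval the standard. On the plan's own rates, 20 children per arm give about 4.2, 2.9 and 0.5 IGA successes (20 × 20.93%, 14.63% and 2.7%) in the 1%, 0.3% and vehicle groups. With so few responders, the dose-response objective will lean heavily on the continuous scales. Protocol 3.3.1 does not replace withdrawals.

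**Working it through.** **The plan's own figures.** Protocol 7.1 gives probabilities of 96.2%, 88.3%, 71.5% and 60.6% for orderings of the IGA success rates. Exact enumeration of independent binomial counts with n = 20 per group gives 95.5%, 86.9%, 71.5% and 58.9%, within 2 points each time. These figures concern IGA success only. The documents give no figure for interval width or coverage on the continuous scales.

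**Inputs from the documents.** 60 children, three arms of 20 (Protocol 7.1); minimisation (Protocol 3.6); ANCOVA with treatment and own baseline (SAP 10.1.2); two-sided 95% intervals (SAP 6.6).

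**Assumed inputs.** Two binary factors, baseline IGA and age <7; the favoured arm chosen with probability 0.8; R², the share of the variance left after own baseline that the factors explain, ranged from 0 to 0.20.

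**Formula.** If the residual variance after own baseline is 1, the planned model's standard error for a difference between two arms of 20 is about √(2/20) = 0.316. The true standard deviation under minimisation is about √(2(1 − R²)/20), because the factors are nearly balanced. The planned model has 60 − 4 = 56 residual degrees of freedom and the model with two binary factors has 54. So:

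width ratio (planned / with factors) = [t(56) / t(54)] / √(1 − R²), where t(56)/t(54) = 2.0032/2.0049 = 0.9992.

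- R² = 0.05: 0.9992/√0.95 = 1.025
- R² = 0.10: 0.9992/√0.90 = 1.053
- R² = 0.20: 0.9992/√0.80 = 1.117

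**Simulation.** Both simulations fit the ANCOVA at one timepoint. A: 4,000 runs per setting, baseline IGA 50:50, 25% aged <7. B: 1,500 runs per setting, 60% moderate, 30% aged <7; its ranges span correlations of 0 and 0.5 between own baseline and baseline IGA. The A width ratios are the reciprocals of 1.005, 0.979, 0.953 and 0.895.

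| Assumed R² | Width ratio: formula | A | B | Coverage %, planned / with factors: A | B |
|---|---|---|---|---|---|
| 0 | 0.999 | 0.995 | 0.995–0.998 | 95.2 / 95.3 | 94.2–94.9 / 94.5–95.0 |
| 0.05 | 1.025 | 1.021 | 1.023–1.024 | 95.3 / 94.9 | 95.8–96.5 / 95.2–95.9 |
| 0.10 | 1.053 | 1.049 | 1.050–1.054 | 95.9 / 95.2 | 95.3–96.2 / 94.5–94.9 |
| 0.20 | 1.117 | 1.117 | 1.116–1.117 | 97.1 / 95.1 | 96.7–97.3 / 94.6–95.5 |

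The Monte Carlo standard error of a coverage near 95% is √(0.95 × 0.05/4000) = 0.34 points in A and √(0.95 × 0.05/1500) = 0.56 points in B.

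**Where the excess width comes from.** In B at R² = 0.20 and zero correlation, the planned interval has mean width 1.274, so its mean standard error is 1.274/(2 × 2.0032) = 0.318. The estimates themselves have standard deviation 0.283, against 0.279 with the factors in the model. Adjustment hardly moves the estimate. It mainly brings the reported standard error into line with the precision that the allocation already delivers.

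**Limits.** Protocol 3.7.4.3 and 3.7.4.4 restrict VAS and VRS to ages 7 to 14. With at least 8 of 60 children aged 2 to 6, at most 52 contribute there, and an age <7 factor is constant. The table does not transfer to those two scales as it stands. The MMRM was not simulated; the same reasoning applies to it.

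**The case against.** A reader might infer that the five models contain no allocation factor and that their intervals are therefore too wide. The documents support neither statement without conditions. The factors are in a specification outside these documents, and one of them could be a baseline score that is already its own model's covariate. If site were the only factor, omitting it would be defensible and the models would not change. This part of the objection stands, but it has a limit. The five scales have five different baselines, so any one factor can be directly present in the models of at most one scale. The VAS and VRS baselines do not exist for ages 2 to 6 and so cannot be factors for all children.

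The size is also uncertain. No document figure supports any particular R². Baseline IGA and EASI both grade erythema and infiltration/papules, so baseline EASI already carries some of what IGA would add. At R² = 0.05, simulation A cannot distinguish the planned coverage from 95%.

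Nor is this a departure of the SAP from the protocol. Own-baseline adjustment is a deliberate choice made in both documents, and a reasonable one.

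Finally, the endpoints are secondary, the primary endpoint is descriptive adverse-event incidence, no decision rule depends on interval width, and the error is conservative. All of that stands and limits the weight of the point. It does not argue against a correction that costs almost nothing.

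**Conclusion.** The point holds conditionally. Allocation is by minimisation, and the models for these five scales adjust for nothing beyond own baseline. If the factors are prognostic beyond that baseline, the 95% intervals are about 2%, 5% or 12% wider than needed at an assumed partial R² of 0.05, 0.10 or 0.20, with coverage of about 97% at 0.20. If they add nothing, the intervals are not too wide. In terms of reported width, R² = 0.20 corresponds to about 25% more children (1.117² = 1.25) and R² = 0.10 to about 11% (1.053² = 1.11).

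These sizes assume two binary factors, near-complete balance and 60 evaluable children at a single timepoint. The loss is one of reported precision on secondary endpoints. There is no bias and no inflation of false positives. The change is worth making, but no primary conclusion depends on it.

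**What to change.** Before database lock, and from the allocation specification rather than from outcome data, amend SAP 10.3 and 10.1.2 to 10.1.7:

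- Name the minimisation factors.
- State that the MMRM and ANCOVA models for EASI, VAS, VRS, POEM and affected BSA, including the percent-change analyses, contain those factors as fixed effects in addition to the variable's own baseline.
- List the exceptions: a factor that is already the model's baseline covariate; site, if it is a factor, because about 8 levels in 60 children cost too much; and any age <7 factor in the VAS and VRS models, where it is constant.
- Keep the IGA-success analysis stratified by baseline IGA as planned, because responders will be few.

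The cost is SAP wording and one degree of freedom per binary factor; the total depends on how many factors there are. If two binary factors prove not prognostic, the intervals widen by about 0.5% (0.2% to 0.5% across the simulations). SAP section 4 has the plan finalised before database lock, which leaves room for the change.

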##### **(2) Assessment period (treatment period)**

For subjects meeting the inclusion criteria and not meeting any of the exclusion criteria at the baseline examination, the period between the day of the starting baseline examination and the day of the Week 4 examination (or the day of discontinuation) is defined as the assessment period. The IMP will be administered to the treatment area from the day of the baseline examination twice daily for 4 weeks. After the baseline examination, the examination will be performed at Weeks 1, 2, and 4.

[figure not shown]
If a subject discontinues the IMP administration between the day of the baseline examination and the Week 4 examination, a withdrawal examination will be performed for that subject.

##### **(3) Post-treatment observation period**

The period from completion of the Week 4 examination to the day of the examination 2 weeks after the last IMP administration is defined as the post-treatment observation period. Examinations will be performed at 2 weeks after the last IMP administration. If any adverse event remained not recovered at the examination 2 weeks after the last IMP administration (or by the day of the last examination if the examination 2 weeks after the last IMP administration was not performed), it should be followed up according to the specifications.

(4) Trial period

The trial period for individual subjects is from the day of obtaining informed consent from the subject’s legal guardian to the day of trial discontinuation or completion and does not include the follow-up period.

**Figure 3.1-1 Trial Design Schematic**

### 3.2 Methods of Administration

#### 3.2.1 Dose, Regimen, and Treatment Period

The 0.3% or 1% formulation or the vehicle of OPA-15406 ointment will be administered twice daily (approximately 12 hours apart between morning and night administration) for 4 weeks. The amount of IMP (g) per dose is calculated as follows.

- 1) The subject's BSA (m^2) will be calculated based on height and body weight at the screening examination, using the following equation.

$$BSA (m^2) = \sqrt{\frac{Ht (cm) \times Wt (kg)}{3600}}$$

BSA = body surface area;  
Ht = height; Wt = body weight  
(Mosteller 1987)

- 2) The treatment area will be specified (see "3.2.2 Treatment Area").
- 3) The amount of IMP (g) per dose will be calculated as "subject's BSA (m^2)" × "treatment area (%)" × "10 g/m^2."  
Example: In case of a BSA of 0.7 m^2 and an affected BSA of 32%: 0.7 m^2 × 0.32 × 10 g/m^2 = 2.24 g

[Rationale for treatment period]

The Guidelines for Management of Atopic Dermatitis specify that "Patients should be evaluated for treatment effects about once every 1 to 2 weeks, especially to maximize the drug effects and to minimize any adverse drug reaction, and if necessary, the drugs and treatment methods should be adjusted. If no particular improvements are observed, or if any abnormal change is detected in the symptoms during about a month of remission induction therapy, referral of the patient to a more specialized institution may be considered." In consideration of this standard AD treatment policy, the treatment period of this trial is established as 4 weeks. In the phase 2 trial outside Japan (271-12-205), while no significant difference was observed the incidence of success in IGA (rate of subjects with an IGA score of 0 or 1 with an improvement by at least 2 grades) at Week 4, which was the primary efficacy endpoint between the 0.3% OPA-15406 group and the vehicle group (p = 0.0690, CMH test), the 1% OPA-15406 group showed a significantly higher incidence of success in IGA compared to the vehicle group (p = 0.0165, CMH test), and no particular concerns were raised over safety up to Week 8.

